Official Title: Developing a Lifestyle Intervention to Reduce Body Weight for Obese African American Men Living in the Rural South

NCT #: NCT05530980

Date: 12/19/2023

Protocol

The primary objective of this study to test the feasibility and acceptability of a theoretically-based 12-week behavioral weight management intervention tailored to Black men living in the rural South. A total of 15 Black men living in Orangeburg County South Carolina or neighboring rural counties will be recruited. Primary outcomes of interest for this single group pretest-posttest feasibility study include the number of Black men who express interest in the study, the number who are eligible/ineligible, the length of time needed to enroll the desired sample size, attendance, and attrition. Change in weight and weight-related behaviors (physical activity and dietary behaviors) will be secondary outcomes and will be measured at baseline and upon completing the intervention. Participants who complete the intervention will be invited to complete a post-intervention focus group interview to provide feedback on the intervention (e.g., motivation for participating, program effectiveness and enjoyment, facilitators and barriers to participation, recommended improvements). This interview may be held virtually or in-person based on participant preferences. The interview will be audio-recorded and transcribed by a professional transcriptionist.

Many participants in the qualitative study that informed the development of the intervention noted that safety and convenience were two important considerations in program planning. In addition, men noted a preference for programs that incorporated physical activity during meeting sessions. Based on these considerations and the status of the COVID-19 pandemic at the time the intervention was developed, publicly available walking track/outdoor areas were deemed to be a feasible and acceptable location for intervention delivery. In the event of inclement weather, meeting sessions will be held at a local YMCA.

The table below shows a general overview for each of the core 12-week sessions. In brief, participants will be taught core principles of weight loss and behavior change. Participants will be provided with Fitbits and will be asked to self-monitor their physical activity throughout the program. In addition, they will be asked to create Fitbit accounts and to support and compete with other men in the program. Participants will also be asked to track their dietary intake using either paper-based tracking forms or a method of their choice (e.g., food tracking app such as MyFitnessPal). A simple kitchen scale will be provided to those needing one to facilitate accurate dietary tracking. Participants will also be highly encouraged to monitor their weight throughout the program using a bathroom scale. A bathroom scale will be provided to those needing one. YMCA memberships will also be offered for the duration of the study or financial support to cover YMCA memberships will be provided to help participants reach physical activity goals.

Sample Meeting Session

Activity	Description	Duration
Welcome & educational session	Content addressed by facilitator; facilitated discussion of content	10 minutes
Progress reports & social support	Participants provide update on weekly progress (e.g., PA, diet, weight)	10 minutes
Warmup walk with socialization	Timed walk around track, field, or other PA destination; opportunity for socialization with peers and facilitator	10 minutes
Competitive activity	Group-based competitive activity (specific activities to be planned with participants but may include receiver drills, 40-yard dash, 2-hand touch football, pushups, etc.)	15 minutes
Cooldown walk with socialization	Timed walk around track, field, or other PA destination; opportunity for socialization with peers and facilitator	5 minutes
Wrap-up and future planning	Q/A session about content; next week goal setting	10 minutes

Surveys/Instruments

Anthropometric measures (weight, body mass index, and waist circumference) will be measured during in-person visits at baseline, approximately 1 week after completing the intervention, and approximately 3 months after completing the intervention. Weight and height will be measured using a portable digital scale and stadiometer, and waist circumference will be measured using anthropometric measuring tape. Blood pressure will be measured in duplicate using a portable automatic monitor. Moderate-vigorous physical activity (MVPA) will be assessed using Actigraph accelerometers worn on the wrist. Dietary intake will be assessed at each time point using three 24-hour dietary recalls performed by the PI or research assistant using the Nutrition Data System for Research software. Several psychosocial factors will be assessed. Social support for exercise will be assessed using a 13-item scale developed by Sallis and colleagues, and self-efficacy for exercise using a 16-item Self-Efficacy for Exercise Questionnaire adapted from Garcia and King. Motivation for healthy eating will be assessed using 15 items of the Treatment Self-Regulation Questionnaire (TSRQ), and motivation for physical activity will be assessed using the 24-item Motivation for Exercise Scale. Motivation for weight loss will be assessed using an 8-item weight control motivation scale developed by Stotland and colleagues. Environmental support for PA will be assessed using the 33-item Rural Active Living Perceived Environmental Support Scale (RALPES). Subscales of the Neighborhood Environment Walkability Scale (NEWS) will be used to assess neighborhood surroundings and neighborhood safety. Relatedness to others in physical activity will be assessed using a 6-item scale developed by Wilson & Bengoechea. A standard sociodemographic questionnaire will be used to assess various variables of interest including participants' age, living arrangements, education, income, and

insurance status. A generic medical history questionnaire will be used to assess various acute and/or chronic conditions that participants may have.

Upon completion of the 12-week program, an acceptability survey will be administered to participants along with the other post-intervention measures. A focus group interview will be held soon after program completion for participants to provide feedback on the intervention (e.g., motivation for participating, program effectiveness and enjoyment, facilitators and barriers to participation, recommended improvements).

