Official Title: Developing a Lifestyle Intervention to Reduce Body Weight for Obese African American Men Living in the Rural South

NCT #: NCT05530980

Date: 12/19/2023

Statistical Analysis Plan

Data on the number who express interest in the study will be tracked using a simple Microsoft Excel spreadsheet. Data on those who are eligible/ineligible will be collected using an eligibility form and an enrollment tracking spreadsheet. The length of time needed to enroll the desired sample size will be determined based on the first day of recruitment efforts until all men have provided signed informed consent. Attendance rates will be calculated as the number of sessions attended/total sessions, and >75% attendance will be deemed acceptable. Attrition will be determined by examining the number of rural men who enrolled versus completed the weight loss intervention, and <20% attrition will be deemed acceptable. Simple descriptive statistics will be used for data analysis of primary study outcomes.

Changes in secondary outcomes from baseline to 4 and 6 months will be examined using repeated measures ANOVAs. A two-tailed level of significance at .05 will be used for all analyses.

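### The plan does not provide for measuring men who stop attending, so the secondary change estimates will probably describe completers and may be too favourable

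*Protocol*

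**What the plan says.** The protocol's opening section says that the secondary outcomes, change in weight and in activity and dietary behaviours, "will be measured at baseline and upon completing the intervention". Under Surveys/Instruments, the anthropometric visits after baseline fall "approximately 1 week after completing the intervention, and approximately 3 months after completing the intervention". Diet follows the same schedule: "Dietary intake will be assessed at each time point using three 24-hour dietary recalls". That section gives no separate timing for accelerometry, so the anchor for activity comes from the opening section. The protocol's closing paragraph adds: "Upon completion of the 12-week program, an acceptability survey will be administered to participants along with the other post-intervention measures".

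The SAP states: "Attrition will be determined by examining the number of rural men who enrolled versus completed the weight loss intervention". It accepts attrition below 20%. For the secondary outcomes it says: "Changes in secondary outcomes from baseline to 4 and 6 months will be examined using repeated measures ANOVAs".

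Neither document defines completion, says whether a man who stops attending is invited to the outcome visits, names an analysis set for the change scores, or says how missing values are handled.

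**The concern.** Every post-baseline anchor in the protocol is completion. The SAP's attrition measure treats completion as something each man does or does not do, and so does the protocol when it limits the focus group to men who complete. On that usage, a man who stops at week 5 never reaches the event from which his visits are timed.

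This is first a question of data collection. A weight that is not measured cannot be recovered at analysis; a model can only make assumptions about it. Men who leave a weight-loss programme may well have lost less than those who stay. If they are not measured, the reported change describes men who finished, not men who enrolled, and is likely to look better than the programme's effect on everyone who started. The acceptability survey has the same anchor, so the views of men who left could be missed too.

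**Working it through.** The documents give no figure for expected change or for power, so there is nothing to reproduce. The check has three parts.

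**1. Who would be measured.** The anchors are the end of the intervention (opening section), about 1 week and about 3 months after completion (Surveys/Instruments), and completion of the programme (closing paragraph). The SAP contrasts enrolled men with completers. If completion is individual, a non-completer has no visit date. If it means the calendar end of the programme, he has one, but no sentence says he is invited. Under either reading, a repeated measures ANOVA in its standard form uses only men with all time points, so a man with only a baseline value drops out. So does a completer who misses one visit.

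**2. Size of the possible distortion.** Inputs: N = 15 ("A total of 15 Black men living in Orangeburg County South Carolina or neighboring rural counties will be recruited") and the SAP's limit of under 20% attrition. Assumptions: leavers have zero mean change, and, for scale only, completers lose 4.0 kg on average. Neither is in the documents. With d leavers:

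- all-enrolled mean = completer mean × (15 − d)/15
- overstatement factor = 15/(15 − d)

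| Leavers d | Attrition | Under 20%? | Men left | Factor | All-enrolled mean (kg) |
|---|---|---|---|---|---|
| 1 | 6.7% | yes | 14 | 15/14 = 1.07 | 3.73 |
| 2 | 13.3% | yes | 13 | 15/13 = 1.15 | 3.47 |
| 3 | 20.0% | no | 12 | 15/12 = 1.25 | 3.20 |
| 5 | 33.3% | no | 10 | 15/10 = 1.50 | 2.67 |

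If leavers changed as much as completers, the factor would be 1. If they gained weight, it would exceed the values shown.

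For the chance of 3 or more leavers, take X ~ Binomial(15, p). P(X ≥ 3) is 18.4%, 60.2% and 87.3% at assumed true dropout rates p of 10%, 20% and 30%.

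**3. Whether the SAP's time labels settle the matter.** A month is 365.25/12/7 = 4.348 weeks.

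- First visit: (12 + 1)/4.348 = 2.99 months after the programme starts. The SAP says 4 months, which is 4 × 4.348 = 17.4 weeks.
- Second visit: 12/4.348 + 3 = 5.76 months, which fits the SAP's 6 months.

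The 4-month label fits the first visit only if about a month separates baseline from the first session, and the documents do not say so. The opening section also mentions only one post-baseline time.

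**The case against.** A reader might infer that the protocol excludes non-completers from measurement, or that the study was designed as a completers-only analysis. The documents support neither:

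- No sentence says that men who stop are not measured.
- The closing paragraph speaks of completion of the 12-week programme, which can mean its calendar end.
- The only step expressly limited to completers is the focus group. That contrast suggests the outcome measures were not meant to be limited in the same way.
- The SAP's 4 and 6 months run from baseline, a clock that does not depend on any man's completion.

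These points stand, and they are why the concern is put as a likely result. They do not remove it. The SAP labels time points without saying who attends them, and its first label does not match the protocol. Study staff could reasonably follow either reading.

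On size, the direction of bias is plausible but not shown. With 2 leavers the illustrative gap is 4.0 − 3.47 = 0.53 kg. With an assumed SD of 4 to 5 kg, the standard error for 13 men is 4/√13 = 1.1 to 5/√13 = 1.4 kg, so the gap is under half a standard error. The factor of 1.50 needs attrition that the plan would itself call unacceptable. This also stands: at accepted attrition, sampling error is the larger problem. But sampling error has no preferred direction, whereas this distortion probably does.

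It is also fair that a man with only a baseline value can enter a mixed model. He does so only under an assumption about his missing weights, so this does not replace measuring him.

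**Conclusion.** The concern holds as a gap in provision. The plan does not say that men who stop attending are to be measured. With its anchors and its ANOVA, the secondary change estimates will probably reflect completers. They may be too favourable, by a factor of 1.15 at the highest attrition the SAP accepts and 1.25 at 3 leavers. Both factors rest on the assumption that leavers have zero mean change and remain unmeasured.

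The reach is limited. The five listed primary outcomes (interest, eligibility, enrolment time, attendance and attrition) do not depend on these visits. The change scores are secondary outcomes in an uncontrolled study of 15 men. The point still deserves action before outcome data are collected, because it decides which data will exist and costs little to settle.

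**What to change.** In the protocol, under Surveys/Instruments:

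- Anchor both follow-up visits to a date that does not depend on individual completion: either the last scheduled session of the man's group or a fixed time from baseline. Apply the same anchor to accelerometry, dietary recalls and the acceptability survey.
- State that every enrolled man is invited to both visits whatever his attendance, unless he withdraws consent.
- Align the opening section and the closing paragraph with this.

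In the SAP:

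- Reconcile the 4 and 6 months with the protocol's visits, and state the day from which months are counted.
- Define completion of the intervention. Report stopping the sessions separately from missing an outcome visit; this gives two feasibility figures where the plan now gives one.
- Analyse change in all enrolled men with available data, for example with a mixed model, in place of an ANOVA that drops men missing a time point. State the missing-data assumption and report how many men contribute at each visit.

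The cost is a few sentences in each document and the work of contacting and measuring a few men who stopped. Some will decline, so the result will still be an available-case estimate, though a fuller one. The reported mean change may be less favourable. The sample size, the intervention and the listed primary outcomes do not change.

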Official Title: Developing a Lifestyle Intervention to Reduce Body Weight for Obese African American Men Living in the Rural South

NCT #: NCT05530980

Date: 12/19/2023

Statistical Analysis Plan

Data on the number who express interest in the study will be tracked using a simple Microsoft Excel spreadsheet. Data on those who are eligible/ineligible will be collected using an eligibility form and an enrollment tracking spreadsheet. The length of time needed to enroll the desired sample size will be determined based on the first day of recruitment efforts until all men have provided signed informed consent. Attendance rates will be calculated as the number of sessions attended/total sessions, and >75% attendance will be deemed acceptable. Attrition will be determined by examining the number of rural men who enrolled versus completed the weight loss intervention, and <20% attrition will be deemed acceptable. Simple descriptive statistics will be used for data analysis of primary study outcomes.

Changes in secondary outcomes from baseline to 4 and 6 months will be examined using repeated measures ANOVAs. A two-tailed level of significance at .05 will be used for all analyses.

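### Repeated measures ANOVA drops a man who misses the last visit even from the baseline-to-post change; a mixed model on all observed visits is a cheap improvement

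*SAP*

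**What the plan says.** The whole plan for the secondary outcomes is the SAP's second paragraph: "Changes in secondary outcomes from baseline to 4 and 6 months will be examined using repeated measures ANOVAs", followed by "A two-tailed level of significance at .05 will be used for all analyses". It names no analysis set, missing-data rule, visit contrast, confidence interval or sphericity correction.

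The Protocol's opening paragraph describes a "single group pretest-posttest feasibility study" and says: "A total of 15 Black men living in Orangeburg County South Carolina or neighboring rural counties will be recruited". Primary outcomes are feasibility measures, summarised descriptively. The SAP's attrition criterion ("<20% attrition will be deemed acceptable") compares men enrolled with men who completed the intervention. It does not count a man who finishes the programme and then misses a measurement visit.

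The visits are described in three ways:

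- Protocol, opening paragraph: change in weight and weight-related behaviours "will be secondary outcomes and will be measured at baseline and upon completing the intervention", which is two visits.
- Protocol, Surveys/Instruments: anthropometry "at baseline, approximately 1 week after completing the intervention, and approximately 3 months after completing the intervention", which is three visits.
- SAP: baseline, 4 months and 6 months.

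**The concern.** A three-level within-subject ANOVA needs a complete row for each man. A man weighed at baseline and after the programme, but not at the last visit, drops out of the analysis altogether, including the comparison for which his data are complete.

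Two consequences follow. If missing the last visit has nothing to do with outcome, the estimate stays unbiased but loses men it need not lose, which matters with 15. If men who lost less weight by the end of the programme are less likely to return, the men left are the better responders, and mean loss is overstated at both later visits. Nothing in the documents shows that this will happen, but nothing in the plan guards against it.

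The stakes are limited to the weight-change estimate, and those for the other secondary outcomes, that the study reports. The feasibility results are unaffected.

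**Working it through.** The plan contains no power, SD or effect-size figure, so there is none of its own to reproduce.

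**1. Does the ANOVA drop these men?** A standard repeated measures ANOVA routine was given 15 men, 3 without the last visit. It refused the unbalanced data and ran only on the 12 complete men (denominator df (12 − 1) × (3 − 1) = 22), although all 15 had baseline and post values. A mixed model used all 45 − 3 = 42 observed values.

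**2. Precision cost for the baseline-to-post change, random dropout.** With k of 15 men missing only the last visit, the standard error rises by up to √(15/(15 − k)):

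| k | Men used | Observed values discarded | SE ratio |
|---|---|---|---|
| 2 | 13 | 4 of 43 | √(15/13) = 1.074 |
| 3 | 12 | 6 of 42 | √(15/12) = 1.118 |
| 5 | 10 | 10 of 40 | √(15/10) = 1.225 |

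**3. Possible bias.** Assumptions, none from the documents:

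- True mean loss is 3 kg at both visits. The first change has SD 4 kg, with a further independent SD of 3.5 kg to the last visit.
- 13 of 15 men reach the first post-programme visit. Losing 2/15 = 13.3% is the most that meets the attrition criterion, since 3/15 is exactly 20%. That criterion is a feasibility limit, not a forecast.
- The log-odds of missing the last visit rise by 0.20 or 0.35 per kg of poorer first change.

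The likelihood estimate of the first change is the mean over all 13 men. For the last change it is ȳ₂(complete) + b × [ȳ₁(all) − ȳ₁(complete)], where y₁ and y₂ are the two changes and b is the slope of y₂ on y₁ in complete cases. Here b averages 1, so complete-case bias is the same at both visits. Results from 20,000 simulated trials per scenario:

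| Missing last visit | Complete-case loss, slope 0.20 | Complete-case loss, slope 0.35 | Likelihood |
|---|---|---|---|
| 10% | 3.3 kg | 3.5 kg | 3.0 kg |
| 20% (10.4 complete on average) | 3.6 kg | 3.9 kg | 3.0 kg |
| 28% | 3.8 kg | 4.2 kg | 3.0 kg |

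At 20% missing:

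- The complete-case SE is 1.19 or 1.14 kg for the first change and 1.62 or 1.58 kg for the last.
- The complete-case 95% CI covers the true first change 93% or 90% of the time, and the last change 94% or 92%.
- Variance, complete-case over likelihood, under random dropout: 1.28 (first change) and 1.12 (last). Under selective dropout the last-change ratio is 1.04 or 0.96, so precision there barely changes.
- Root mean squared error for the last change is 1.6 kg by likelihood against 1.7 to 1.8 kg by complete cases, including under random dropout.

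A separate simulation in SD units gave the same direction. With 3 of 15 men missing, correlation 0.8 to 0.9 and a true change of −0.20 SD, complete cases gave −0.33 and −0.31 for the first change; a random-intercept mixed model gave −0.19 and −0.20.

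**4. Where the mixed model does not help.** If the 2 early leavers are the poor responders (0.35 per kg) and later dropout is random, both methods give 3.6 kg. If missing the last visit depends on the unseen last weight (20% missing), likelihood still gives 3.0 kg for the first change but 3.46 or 3.66 kg for the last; complete cases give 3.98 or 4.35 kg.

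**5. Sphericity.** Under the assumed covariance, epsilon is 0.79. The uncorrected F test has type I error 6.2% (6.0% to 7.3% over four covariance patterns); with the Greenhouse-Geisser correction it is 4.6% to 5.0%. This is a minor point.

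**6. Visit times.** Twelve weeks plus 1 week is 13 weeks, or 3.0 months from programme start. Twelve weeks plus 3 months is 5.8 months. The SAP's 4 months is 17.4 weeks. The last visit fits the 6-month label roughly; the first post-programme visit does not fit the 4-month label if time runs from programme start.

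**The case against.** The strongest objection is that the text does not force this reading. The plural ANOVAs could mean separate baseline-to-4 and baseline-to-6 analyses, and then a man who misses only the last visit stays in the first comparison. That is possible, but the plural could equally mean one ANOVA per outcome, and the SAP does not say. Even on the favourable reading, the last-visit estimate rests only on men seen at that visit.

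Second, the harm is assumed. No document gives a dropout rate or mechanism, and the attrition criterion does not measure last-visit loss. With an SD of 4 kg, the slopes of 0.20 and 0.35 are odds ratios of exp(0.8) ≈ 2.2 and exp(1.4) ≈ 4.1 per SD, so the upper case is strong selection. The bias is also smaller than the standard error, and about 20% × 13 = 2.6 men are involved. All of this stands and limits the weight of the point.

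Third, the first-change problem needs no mixed model: a paired analysis of everyone seen at the first visit has 95% coverage. That is true. What the mixed model adds is removal of last-visit bias when missingness depends on observed values, and a smaller last-visit error in the 20% scenarios.

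Fourth, only weight was simulated, and convergence of an unstructured REML fit with 13 to 15 men was not tested for every outcome. This also stands, and is why a fallback must be pre-specified.

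**Conclusion.** The concern holds as a cheap improvement, not as a flaw that threatens the study. In its standard form the only method named for the secondary outcomes discards observed baseline-to-post data from any man who misses the last visit, and nothing else in the documents repairs this. If dropout is unrelated to outcome, the cost is precision alone. If it follows poor early loss, a true 3 kg loss would be reported as about 3.6 to 3.9 kg at 20% missing (3.3 to 4.2 kg across 10% to 28%). These figures depend on the assumed SDs, effect, first-visit numbers and dropout slopes. Confidence is medium, because the missingness mechanism is unknown and the SAP's wording leaves room for another reading.

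**What to change.** First reconcile the visit schedule across the Protocol's opening paragraph, its Surveys/Instruments section and the SAP, and state the time origin. Then, for each secondary outcome, replace the ANOVAs with:

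- a linear mixed model on all observed visits, with visit as a categorical fixed effect and baseline included as one of the outcomes;
- unstructured within-man covariance with a pre-specified simpler fallback, fitted by REML with small-sample degrees of freedom such as Kenward-Roger;
- the baseline-to-post and baseline-to-follow-up changes with 95% CIs, and the number of men observed at each visit;
- complete-case results as a sensitivity analysis. If ANOVA is kept for that purpose, name the contrasts and a sphericity correction.

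The SAP should state the limits: the model removes bias only if data are missing at random, men with baseline only add almost nothing on change, and loss that depends on unseen weight is not fully corrected.

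The cost is a few SAP sentences and a little more analysis of data already planned, with no new visits or men. The downsides are that the fallback may be needed at this sample size, precision at the last visit barely improves, and the model does not help if poor responders leave before the first post-programme visit.

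### Does testing change in weight, activity and diet at two-tailed .05 in 15 uncontrolled men, with no planned interval or exploratory label, call for a change to the SAP?

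*SAP*

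**What the plan says.** The opening paragraph of the Protocol sets a feasibility and acceptability objective, a recruitment target of 15 men and a "single group pretest-posttest feasibility study". The primary outcomes are interest, eligibility, time to enrol, attendance and attrition. The clinical measures come second: "Change in weight and weight-related behaviors (physical activity and dietary behaviors) will be secondary outcomes".

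The SAP treats the two tiers differently. For the primary tier, "Simple descriptive statistics will be used for data analysis of primary study outcomes". For the secondary tier, "Changes in secondary outcomes from baseline to 4 and 6 months will be examined using repeated measures ANOVAs", followed by the general statement that "A two-tailed level of significance at .05 will be used for all analyses". Those last two sentences are the whole secondary analysis plan. Neither document mentions a confidence interval, an exploratory status, a multiplicity rule, a power calculation or a reason for choosing 15.

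**The concern.** The only output that the SAP names for the secondary outcomes is a significance test, and in so small a group such a test is weak in both directions. A non-significant result would be compatible with no change or with a large one. A single significant result among several could be chance, and without a control group even a genuine change could not be credited to the programme. A later trial would need the size of the change and its uncertainty, and the plan does not promise either. Applying .05 to all analyses could also encourage a reader to treat a secondary p-value as a finding of efficacy.

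The SAP also leaves open whether each outcome gets one overall test across the visits or a separate contrast with baseline at each follow-up. The number of tests is therefore not fixed. At stake is how the secondary results are read. The primary feasibility outcomes do not rest on these tests.

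**Working it through.** **Inputs from the documents.** There are 15 men and three secondary domains: weight, physical activity and diet (Protocol, opening paragraph). The level is two-tailed .05, with three time points (SAP). The attrition criterion is that "<20% attrition will be deemed acceptable" (SAP): 2/15 = 13.3% meets it and 3/15 = 20.0% does not, so 13 is the fewest programme completers that pass.

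**Inputs not in the documents.** These are the SD of change, the correlation between domains and the number of diet variables. I work in units of the SD of change, assume one variable per domain, and take the correlation from 0 to 0.7. The plan states no power or effect size, so there is no figure of its own to reproduce.

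**False positives when nothing changes.**
- One test per domain, independent: 1 − 0.95³ = 0.143.
- One ANOVA F test per domain, simulated (40,000 runs, n=15, sphericity), at correlations 0, 0.3, 0.5 and 0.7: 0.141, 0.137, 0.128 and 0.112.
- Two contrasts with baseline per domain, six tests, independent: 1 − 0.95⁶ = 0.265. Allowing for the shared baseline, simulation gives 0.247, and 0.197 if the domains also correlate at 0.7.
- The same contrasts read only after a significant ANOVA: about 9% (correlation 0.7) to 12% (independent).

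The plain reading of the SAP is one ANOVA per outcome, which gives 11% to 14%. The 20% to 26.5% range needs six unprotected contrasts, which the SAP does not name.

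**Precision and power for one change from baseline.** The half-width is t(.975, n−1)/√n; power comes from the noncentral t for a paired test.

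| n | Half-width (SD of change) | Change giving 80% power | Power at 0.5 SD (illustration) |
|---|---|---|---|
| 15 | 2.145/3.873 = 0.554 | 0.778 SD | 0.438 |
| 13 | 2.179/3.606 = 0.604 | 0.847 SD | 0.382 |
| 10 | 2.262/3.162 = 0.715 | not computed | not computed |

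A result just short of .05 would have an interval from about 0 to twice the half-width: 2 × 0.554 = 1.11 SD at n=15, or 2 × 0.604 = 1.21 SD at n=13.

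Two qualifications apply. First, these are paired t figures. With the ANOVA's pooled error, under sphericity and 2(n−1) degrees of freedom, the half-widths are slightly smaller: 2.048/3.873 = 0.53 at n=15 and 2.064/3.606 = 0.57 at n=13. Second, 13 is not a floor for the analysed sample. The attrition criterion concerns completion of the programme, whereas the section Surveys/Instruments places the anthropometric follow-ups "approximately 1 week after completing the intervention, and approximately 3 months after completing the intervention". Fewer men may attend the later visit, hence the row for n=10.

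**What the gap costs.** The mean change, its interval and the number of men contributing all come from the data that the planned ANOVA uses. Nothing has to be collected or decided in advance to produce them.

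**The case for a change.** The best case for a change is that the exploratory status is only inferred. The SAP never states it, and a .05 rule for all analyses points the other way. Saying that changes will be examined may imply means, but it does not imply intervals. One added sentence would cost almost nothing and would give readers what a later trial needs.

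The factual part stands: neither document states an interval or a label, and a p-value alone would be a poor summary at this size. The harm, however, depends on a reporting choice that the SAP does not make. It does not confine the report to p-values, and it plans no claim from them. On the primary outcomes the .05 sentence has no effect, because those are only described. The remedy is also not quite free: calling the p-values descriptive would conflict with a .05 level for all analyses unless that sentence was rewritten too. The result would be a new label on the same ANOVA and the same data.

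Two neighbouring points are separate and add no weight here. The diet variable is not named. The follow-up times also differ: the Protocol's opening paragraph says that the secondary outcomes "will be measured at baseline and upon completing the intervention", Surveys/Instruments adds a visit about 3 months later, and the SAP gives 4 and 6 months. Those passages should be reconciled in their own right.

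**Conclusion.** No change to the plan follows. The omission is real but minor: it is missing reporting detail in a short SAP, for outcomes already ranked below feasibility in a single-group study. A competent analyst will show mean changes with intervals and the number of men behind each. A competent reader will not attribute an uncontrolled change in 15 men to the programme because p is below .05.

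The size is modest on the natural reading. The chance of at least one false positive is 11% to 14% over three ANOVAs, and the half-width is 0.55 to 0.60 SD of change for 15 or 13 men, widening to 0.72 SD if only 10 attend. The higher false-positive figures apply only if unprotected visit contrasts are tested. All of this assumes one variable per domain and, for the error rates, no true change in any domain and correlations between 0 and 0.7. The conclusion would differ if the sponsor meant to rest an efficacy claim on one of these tests; neither document says so.
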